2.6 Rationale for Outcome Measures Selection

A. Primary objectives: We plan to use the average daily and weekly pain scores determined by the OM Pain App and the average weekly pain scores determined by the BPI short form to assess the efficacy of the study drug combination. Cancer and cancer therapy-related pain estimates vary widely and there is a lack of standardization of pain assessment tools in this area. Studies have shown that real-time assessment of patient-reported pain outcomes improves provider awareness and leads to better management of pain. Further, real-time assessment is very important for the head and neck cancer patient population as these patients are predisposed to specific problems, such as difficulty in articulating and accurately describing pain due to severe mucositis. These issues can be resolved with real-time assessment of pain by a smartphone-based application. To our knowledge, app-based pain assessment of buprenorphine has never been studied on head and neck cancer patients suffering from radiation-induced mucositis pain. Our goal will be to use the VAS-based pain assessment tools on the OM Pain App and BPI short form to evaluate the pain response of the buprenorphine and tramadol combination regimen.

Painful mucositis usually manifests by the third to fourth week of starting radiation and continues four to five weeks after the termination of therapy. Therefore, we decided to follow patients up to 12 weeks after they begin radiation therapy.(4, 17, 30) Mild-intensity mucositis pain can be effectively managed with low-potency pain medications like Tylenol®, NSAIDS, and oral lidocaine. Thus, we plan to initiate treatment with the tramadol

and buprenorphine combination once the patient develops mucositis and a VAS pain score $\geq 4/10$. Earlier pain management studies in radiation-induced mucositis have acknowledged that the pain curve follows a nonlinear pattern during radiation therapy and starts to peak by the fourth to fifth week of radiation therapy. It then plateaus and later drops to a lower level after initiation of long-acting effective pain medications, such as fentanyl or oxycodone. Hence, it is reasonable to use the pain score on the day of treatment initiation as our baseline pain score. (27, 29, 31)

B. Secondary Objectives: Adherence to the prescribed dose and frequency of pain medications is vital to symptom management of radiation-induced mucositis pain. Poor adherence is often associated with worse symptom control and inaccurate assessment of the potency of pain medications. Greater clinical support and research are needed to overcome the challenges of fragmentation in care from clinic to home, with specific attention to adherence and symptom management. We plan to use our pain app to make accurate and real-time assessments of compliance and efficacy of the pain regimen. We will also assess the use of off-protocol pain medications during study period.

We plan to study the impact of radiation-induced mucositis pain on head- and neck-related symptoms and physical activity. This data will be further characterized and evaluated by the MDASI-HN symptom and function tool. Use of other medication like laxatives and antiemetics in conjunction with the study drug combination during treatment can be used as surrogate markers of gastrointestinal side effects associated with the drug regimen. We plan to record these values on a weekly basis and expect its use to decrease by the end of follow-up period. To study the gastrointestinal and cognitive side effect profile of transdermal buprenorphine and tramadol regimen, we plan to use a highly intuitive patient-reported outcome measurement information system tool called PROMIS®. All PROMIS® scales have been validated in cancer patients. We plan to use PROMIS® questionnaires to evaluate the cognitive and gastrointestinal side effect profile of the drug regimen and its impact on quality of life of patients. Incidence and severity of adverse events associated with the study drug regimen, such as constipation, sedation, respiratory depression, and others will also be evaluated, using the CTCAE version 5. We will collect this data to make appropriate and timely symptom-related interventions.

3 STUDY DESIGN

3.1 General Description

This is a single-arm, interventional, supportive care clinical trial for head and neck cancer patients evaluating the role of a TD buprenorphine and tramadol combination in alleviating radiation-induced mucositis pain. This will generate preliminary data to test the feasibility and efficacy of the study drug regimen. The study will also test the clinical usefulness of the smartphone pain app in recording and reporting radiation-induced mucositis pain. Additionally, it will also evaluate the role of symptom and function assessment tools, such as MDASI-HN and PROMIS® in identifying adverse effects related to the study regimen in the setting of chemoradiation therapy.

3.2 Study Procedures

Patients found to be eligible for the study can be screened and enrolled anytime during the first six weeks of radiation therapy. VAS pain scores will be recorded weekly using the BPI questionnaires. They will also be recorded daily, using the pain app from the day of enrollment as outlined in study calendar. Treatment with the study regimen, collection of data from the PROMIS®, MDASI, CTCAE evaluation, and other assessments, such as the opioid drug use log as outlined in study calendar will start once patient develops mucositis and has VAS >4/10 pain score on the OM Pain App and the BPI questionnaire (question 3: your pain at its worst in last 24 hours). Patients usually develop mucositis by the third to fourth week of radiation therapy so we anticipate treatment would begin by fourth week in most patients, but it can start sooner if the patient develops mucositis and has VAS≥4/10 pain. If a patient presents with radiation-induced mucositis pain on the day of enrollment, then, all study procedures, including administering the PROMIS® and MDASI-HN questionnaires, in addition to CTCAE evaluation, will be completed on that day. Visit procedures that were performed as standard of care prior to consent (without the specific intent to make the subject eligible for the trial), may count toward screening tests and eligibility if they are within the screening window of two days. Clinician follow-up will be scheduled weekly (weeks 1–7) and then on weeks 9 and 12. Data can also be collected over phone during the follow-up period (weeks 8–12 from the start of radiation therapy). If a subject stops radiation therapy within the first 7 weeks, weekly visits will continue as scheduled if he/she is on treatment.

3.3 Study Completion

The study is expected to complete its accrual goal in 12 months. The study will reach study completion approximately 18 months from the time the study opens to accrual.

4 SUBJECT PARTICIPATION, DISCONTINUATION, AND WITHDRAWAL

Investigators must follow all MCW IRB requirements and policies regarding subject participation, found here:

<https://www.mcw.edu/HRPP/Policies-Procedures.htm>

4.1 Subject Status

Subject statuses throughout the trial are defined as follows:

- Prescreening: preconsent (subject considering trial or study staff considering a patient for the trial per institutional recruitment methods).
- Screening: the period after the consent, but prior to eligibility confirmation.
- Consented: consented, prior to eligibility confirmation.
- Eligible: the local investigator confirms all eligibility criteria apply.
- On study/enrolled: date eligibility is confirmed.
- On arm: date of enrollment.
- On treatment: first-day treatment with study drug regimen while undergoing radiation
- Off treatment: last day of treatment with study drug regimen
- On follow-up: from the last day of treatment to the end of the follow-up period.
- Off study: follow-up period completed, with no additional data gathered.

- Withdrawn: subject fully withdraws consent (i.e., refuses ALL follow-up, even survival) or is taken off the study by the local principal investigator.

4.2 Prescreening and Screening Log

The MCW study principal investigator regularly reviews screen failure reasons to understand barriers to accrual and consider amending eligibility criteria. Screen failures are defined as participants who were considered for the trial to participate in the clinical trial with or without consent but are not subsequently assigned to the study intervention or enrolled in the study. MCWCC CTO will follow its SOPs regarding prescreening and screening tracking.

4.3 Consent

Investigators or their appropriate designees will identify potentially eligible subjects from their clinics, subject self-referrals, referrals from other clinicians, and/or other IRB-approved recruitment methods. No study conduct, including subject prescreening, can occur until after IRB approval.

A written signed informed consent form (ICF) and a Health Insurance Portability and Accountability Act (HIPAA) authorization must be obtained before any study-specific assessments are initiated. A signed ICF copy will be given to the subject and a copy will be filed in the medical record (per local IRB policies and SOPs). The original will be kept on file with the study records.

4.4 Screening Procedures

Refer to the study calendar of events for details. Patients found to be eligible for the study will be screened and enrolled anytime during first six weeks of radiation therapy. EKG, lab, urine drug screen, medical history and other assessments as per study calendar will be collected on the day of enrollment. This day, patients will complete the BPI questionnaire and the OM Pain App will be installed on their cell phones. Those who do not have a smartphone will be provided with a wifi enabled device with OM Pain App installed on it. Going forward, BPI questionnaire will be completed during weekly clinic visits and daily OM Pain App data monitoring will continue throughout the rest of the treatment and follow up period of 12 weeks. Treatment with the study drug regimen will commence once the patient develops mucositis and has a VAS pain score $\geq 4/10$ on the BPI and pain app. Additional data from PROMIS®, MDASI-HN, opioid and nonopiod drug use log, CTCAE evaluation, calorie requirements, the need for IV hydration, and other assessments will also be recorded as per study calendar.

Based on earlier studies and our clinical practice, we anticipate that most patients will develop moderate intensity pain and require an opioid-based pain regimen by the third to fourth week of radiation therapy.(4, 30) As we will be using the pain score on the day of treatment initiation and not the date of enrollment as our baseline, we don't expect that timing of initiation of drug regimen would have a significant impact on our results.

4.5 Registration Process

Recruitment

Potential study participants will be identified by routine care in the MCW Cancer Center clinics.

Subjects will sign the informed consent form in the cancer center clinics. A team approach will be used whereby physician sub-investigators will discuss and describe the clinical trial with study candidates. The study coordinator will obtain the informed consent from participants and perform study registration. For women of childbearing potential, a negative pregnancy test must be obtained within 24 hours prior to starting radiation therapy. Visit procedures that were performed as standard of care prior to consent (without the specific intent to make the subject eligible for the trial), may count toward screening tests and eligibility if they are within the screening window of two days.

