5.9.3 Daily Intervention

If enrolled, patients can start using the app up to one week prior to radiation therapy for training and practice. Formal data monitoring would only start once patients start study drug regimen. As noted, subjects will receive a preprogrammed alarm four times a day from their smartphones prompting them to directly enter OM pain levels on the device. Patients may submit as many pain entries as they wish beyond the four minimum levels. The software also allows patients to document self-administration of breakthrough pain medication. This event will prompt immediate entry of a pain level and an automatic pain assessment one-half hour later. Because symptoms of mucositis do not commence typically until the third week of radiation therapy, and no sooner than week 2, we don't expect to start data recording earlier than that. Recording of data will cease five weeks (week 12) after the end of radiation therapy at which time mucositis symptoms typically start to resolve and pain symptoms substantially abate (see the schema).

5.9.4 Avoiding Bias: A viewable graphic summary of pain scores will be a functionality of the app but will be disabled in this study to avoid bias of care provider or participant. For the feasibility phase, patients and providers will be blinded to the pain scores and symptoms will be managed with supportive treatments during routine weekly provider visits and symptom-initiated clinical visits.

5.9.5 Monitoring Compliance: The study coordinator will download data and check the equipment weekly for proper functioning and compliance. Patients will be interviewed weekly to assure the device is functioning correctly and that data are being recorded. Compliance with the device use will be assessed by the percent adherence to the device prompted four times daily pain assessment.

Architecture, Framework, and IT Network for Mobile Platforms

Figure 1 Shows the architecture for the proposed iPhone/Android Apps. To ensure data security and confidentiality, web registration was implemented in the Apps for the web server to generate a unique device ID for the purpose of secure information exchange. The Apps will incorporate an intuitive user interface for recording pain severities in order for the patients to engage in the reporting activities. The reported pain data will be uploaded to a secure web server via secure Hypertext Transfer Protocol (HTTPS) to allow for monitoring by the health professionals.

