Radiation toxicity data will be used to associate with OM pain data. All acute and late adverse events from radiation therapy will be recorded and scored for severity using the NCI Common Terminology Criteria for Adverse Events (CTCAE) version 5.0. As noted, a copy of the CTCAE v5.0 can be downloaded from the CTEP home page (<https://ctep.cancer.gov/>). While radiation therapy side effects will be recorded, they will not be reported as adverse events for the purpose of the study, because its purpose is to evaluate the efficacy of the study drug regimen. The radiation therapy will be delivered according to the standard of care and not directed by this protocol.

Chemotherapy Adverse Events

Chemotherapy-related toxicity data will be used to associate with OM pain data. All acute and late adverse events from chemotherapy will be recorded and scored for severity using the NCI Common Terminology Criteria for Adverse Events (CTCAE) version 5.0. Toxicity data will be recorded because cumulative toxicity may have indirect effects on pain perception.

While chemotherapy side effects will be recorded, they will not be reported as adverse events for the purpose of the study, because the purpose of this study is to evaluate the efficacy of buprenorphine and tramadol combination regimen.

The investigator and his or her team will follow the Medical College of Wisconsin policies related to adverse event reporting. This information may be found on the Human Research Protection Program website.

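### Section 4.5 ties the negative pregnancy test to the start of radiation, and women enrolled before mucositis pain develops need no test before the first buprenorphine patch

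*Combined protocol and SAP*

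**What the plan says.** Section 4.5 (Registration Process) sets the timing rule: "For women of childbearing potential, a negative pregnancy test must be obtained within 24 hours prior to starting radiation therapy". The next sentence of 4.5 lets standard-of-care procedures done before consent count toward screening "if they are within the screening window of two days". Section 4.3 says that signed consent "must be obtained before any study-specific assessments are initiated".

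Section 4.4 places enrolment during radiation: "Patients found to be eligible for the study will be screened and enrolled anytime during first six weeks of radiation therapy". Section 5.9.3 hints at earlier entry: "If enrolled, patients can start using the app up to one week prior to radiation therapy for training and practice".

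A second test is listed among the enrolment-day assessments in 4.6. The study calendar shows one hCG, in the screening column. The procedure lists in 4.8 (after study drug starts) and 4.9 (follow-up) contain none.

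Study drug starts when mucositis is present and the pain score reaches 4/10, not at enrolment. Section 4.4 expects most patients to "require an opioid-based pain regimen by the third to fourth week of radiation therapy". Section 3.2 also provides for the other case: "If a patient presents with radiation-induced mucositis pain on the day of enrollment", all study procedures are completed that day.

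Exclusion 16 bars pregnant women, first because of radiation and chemotherapy and then also because of buprenorphine. Section 7.1.6 advises against buprenorphine in pregnancy. Inclusion 9 requires two contraceptive methods, or abstinence, for women of childbearing potential; the two-method option runs from consent to three months after the last dose.

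**The concern.** The timing rule in 4.5 is attached to radiation, while the treatment this protocol gives is buprenorphine with tramadol. This has two consequences.

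First, the rule does not fit the enrolment window. For most women who consent during radiation, the moment at which the test was due has passed and any chart result is too old to count toward screening. Staff must then disregard a mandatory sentence or record a deviation.

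Second, enrolment and first dose are separate events by design, yet testing is attached only to radiation start and enrolment. A woman enrolled early can receive her first patch on a result that is weeks old. What is at stake is an unrecognised early pregnancy being exposed to a drug that the protocol itself gives as a reason for excluding pregnant women.

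**Working it through.** The plan states no figure on this point. The check compares the sections and then counts days.

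**Which tests are required, and when**

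| Source | Required test | Anchor |
|---|---|---|
| 4.5 | Negative test | Within 24 hours before radiation starts |
| 4.6 and calendar | hCG | Enrolment day / screening |
| 4.8, 4.9, calendar weeks 1-12 | None | – |

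No entry is anchored to the first patch.

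**Can 4.5 be met by a woman enrolled during radiation?** Take radiation day 1 as the first fraction. The 4.5 test falls on day 0 or early on day 1. Consent must come before study-specific assessments (4.3), so for a woman consenting after the first fraction the test cannot be a study procedure. A standard-of-care result counts toward screening for two days: 0 + 2 = day 2, or 1 + 2 = day 3. From about day 4 to day 42 (the end of week 6) the chart route is closed as well. A woman enrolled before her first fraction could meet the rule directly.

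**Age of the enrolment test at first dose.** Age = day of first patch − day of test. Weeks 3-4 of radiation are days 15-28; the end of week 6 is day 42.

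| Enrolment test | First patch days 15-28 | First patch day 42 |
|---|---|---|
| Day 1 | 15−1 = 14 to 28−1 = 27 days | 42−1 = 41 days |
| Day 8 | 15−8 = 7 to 28−8 = 20 days | 42−8 = 34 days |
| Day 15 | 15−15 = 0 to 28−15 = 13 days | 42−15 = 27 days |
| Day of first patch | 0 days | 0 days |

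The day-1 row is therefore about 2 to 4 weeks for the expected start, and about 6 weeks for a start at the end of week 6.

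**Is 41 days the ceiling?** Not firmly. Section 4.10 ties the start of study drug to the first six weeks of radiation. Section 5.1 allows it at any time during radiation and describes seven weeks of it, which would give 49 − 1 = 48 days. The figures in the table follow 4.10.

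**Number affected.** The documents give neither the number of women of childbearing potential nor the spread of enrolment times. Assuming 0 to 3 such women among the 20 enrolled, 0 to 3 could have a stale result. Those who already have mucositis pain at enrolment drop out of that count.

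**The case against.** The strongest reply is that the protocol already protects these women. Each is tested at enrolment. Exclusion 16 names the hazards of radiation and chemotherapy first, so a test placed just before radiation has a clear rationale. Inclusion 9 requires contraception or abstinence, and refers to any applicable pregnancy prevention program. Clinician visits are weekly in weeks 1-7. Pregnancy is listed as a serious adverse event (6.1.2), and such events are reportable from consent (6.2.2). No section promises a test at first dose, and a new check must not hold back analgesia from someone in pain.

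Much of this stands, and it limits the point. A reader might infer that women enter untested; 4.6 and the calendar rule that out. A reader might infer that contraception is the only protection in the interval. It is the main preventive one, but SAE reporting and weekly contact also exist. A reader might infer that the radiation anchor is wrong in itself, citing "The radiation therapy will be delivered according to the standard of care and not directed by this protocol". That sentence belongs to the adverse-event reporting rules and does not address pregnancy testing. A reader might also add a week to every gap for enrolment before radiation, but that rests on one sentence about practising with the app, while 3.2, 4.4 and 5.1 place enrolment within radiation.

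What the reply does not supply is a current result at first dose. Contraception is an agreement, and SAE reporting acts only after a pregnancy is recognised. Nor does the reply make 4.5 workable for women enrolled once radiation is under way.

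**Conclusion.** The point holds in a limited form. The 4.5 rule cannot be met as a study procedure by women who consent after radiation has begun. For women enrolled before mucositis pain develops, no test is required before the first patch. The gap is 14 to 27 days for a day-1 test and a first dose in weeks 3-4, shorter for later enrolment, and about zero for those dosed on the enrolment day. The 41-day figure assumes the six-week limit in 4.10. The number of women affected is unknown and could be zero. Severity is minor: this is a safety and consistency matter with no bearing on sample size, power or the primary analysis.

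**What to change.** Keep the enrolment test in 4.6 and the calendar. In 4.5, replace the radiation-anchored sentence with a requirement for a negative hCG within a short stated interval before the first buprenorphine patch, and say that the enrolment test satisfies it if it falls in that interval. Add the same rule as a footnote to the calendar's hCG row. Forty-eight hours is a reasonable choice, and the sponsor could pick another short interval. It should be stated as a rule in its own right, because the existing two-day window was written for procedures done before consent.

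Pre-radiation testing can be left to standard of care, or kept in 4.5 only for women enrolled before radiation starts, so that this check is not lost by oversight.

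The cost is one reworded sentence, one footnote and at most one extra routine hCG per affected woman (0 to 3 tests under the assumption above). The weekly visits already include blood draws, and treatment initiation is already a procedure day because of the oral photographs. A rapid test at that visit avoids delaying pain relief.
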